#### TREATMENT SCHEMA

This study will be a single arm, open-label, phase II trial of sunitinib in patients with metastatic or locally advanced malignant paraganglioma or pheochromocytoma. Oral sunitinib (50mg) will be administered to all patients daily for the first four weeks of a six-week cycle i.e standard scheduling.

#### TRIAL SUMMARY

### **ELIGIBILITY**

- Metastatic or locally recurrent paraganglioma or pheochromocytoma not amenable to curative treatment modalities
- No prior therapy with antiangiogenic agents or multi-targeted tyrosine kinase inhibitors
- > 28 days since prior radiation therapy or major surgery
- Unidimensionally measurable disease
- No known brain metastases
- ECOG performance status: 0-2
- No other concurrent anti-cancer treatment
- No serious medical conditions or cardiac disease (as specified in protocol)
- No uncontrolled hypertension
- Able to take oral medication
- Must be able to stop prohibited selected CYP3A4 inhibitors/inducers prior to starting sunitinib as described in section 5.2

### PRE-TREATMENT EVALUATIONS

- History, physical exam, hematology and biochemistry, urinalysis, toxicity/baseline symptoms, and (if applicable) pregnancy test (within 7 days prior to registration)
- EKG (all patients) and LVEF assessed by MUGA > LLN for patients with prior anthracycline exposure, prior thoracic radiation or NYHA class II cardiac function (within 21 days prior to registration)
- Chest x-ray or CT scan, abdominal and pelvic CT scan, other x-rays/scans as clinically indicated (within 28 days)
- Clinical tumour measurements

TREATMENT: Sunitinib 50 mg will be administered orally daily for 4 weeks out of every 6 weeks.

### ON TREATMENT EVALUATIONS

Day 1 each cycle (within 7 days prior to treatment)

- Physical exam (weight, ECOG PS, vital signs)
- Hematology, biochemistry, urinalysis, TSH, T4
- Toxicity assessment

### Twice weekly, first 3 weeks

• PT/INR/PTT (for patients on low dose anticoagulants or LMW heparin); then as clinically indicated

### Weekly, Cycle 1, then every 2 weeks, cycle 2+

• Blood pressure and heart rate (by nurse or home monitor)

#### Every 2 weeks

• Weight and performance status

### Every 12 weeks, end of every even cycle

- Chest x-ray or chest CT scan, if positive at baseline
- Abdominal and pelvic CT scan (or MRI), if positive at baseline
- Other x-rays/scans, if positive at baseline and as clinically indicated
- Clinical tumour measurements
- Urinary metanephrines, catecholamines or serum chromogranin A (at the end of approximately every 2 cycles)
- EKG; LVEF (MUGA) are only for patients with class II NYHA, prior anthracyclines or prior thoracic radiation

#### **DURATION OF TREATMENT**

Patients should stop protocol treatment in the following instances:

- Intercurrent illness which would, in the judgement of the investigator, affect assessments of clinical status
- Unacceptable toxicity as defined in section 8
- Tumour progression or disease recurrence as defined in section 10
- Request by the patient
- Completion of therapy as outlined in section 12.2

#### 1.0 OBJECTIVES

1.1

To assess the efficacy (response rate) of sunitinib given orally daily for 4 out of every 6 weeks in patients with advanced or metastatic paraganglioma/ pheochromocytoma.

1.2

To assess the toxicity of sunitinib in patients with advanced or metastatic paraganglioma/ pheochromocytoma.

To document effects of sunitinib on markers of biochemical activity of advanced or metastatic paraganglioma/pheochromocytoma

#### 2.0 BACKGROUND INFORMATION AND RATIONALE

Paragangliomas (PGs) are highly vascularized tumours that generally arise from the parasympathetic system in the head and neck, sympathetic ganglia in the thorax and abdomen, and the adrenal medulla. These latter tumors may be functional, secreting catecholamines (pheochromocytomas [PC]).

These tumors can arise as a result of germline mutations in RET, VHL, NF1, and in subunits B, C, or D of the succinate dehydrogenase (SDH) genes, which underlie multiple endocrine neoplasia Type 2 (MEN2), von Hippel–Lindau (VHL), neurofibromatosis Type 1 (NF1), and familial paraganglioma syndromes Type 4 (PGL4), 3 (PGL3), and 1 (PGL1), respectively. Global expression signatures of a large group of 76 hereditary and sporadic primary pheochromocytomas and paragangliomas have been generated. It was found that tumors with VHL and SDHB or D mutations form a single genetic expression cluster, which is distinct from "Cluster 2" pheochromocytomas: those with mutations in RET, NF1, and novel familial pheochromocytoma variants without a known primary genetic defect. In this series, sporadic pheochromocytomas were distributed between the two major clusters. Importantly, novel VHL or SDHB mutations were detected in tumors that aligned with Cluster 1, while RET or uncharacterized deletions were identified in tumors that segregated with Cluster 2 that had not previously been screened. A pathway-enrichment method, gene-set enrichment analysis (GSEA), was then applied to the data to delineate the underlying biological programs embedded in each of these clusters and this suggested that cluster 1 tumors were associated with hypoxia and angiogenesis pathways whilst cluster 2 tumors were associated with pathways representing abnormalities of protein synthesis and translation as well as kinase signalling.

The genetic mechanism thought to underlie the hypoxic phenotype in type 1 tumors suggests that the accumulation of succinate leads to inhibition of proyl hydroxylases that are critical in the hydroxylation and subsequent degradation of hypoxia-inducible factor 1 (HIF-1). A similar mechanism is also evident in tumours with defects in VHL, which is likewise critical in HIF-1 proteasomal degradation. The accumulation of HIF-1 activates transcription of a number of pro-angiogenic factors such as the VEGF family. It is plausible that treatment with a multi-targeted tyrosine kinase inhibitor such as sunitinib may have therapeutic utility in this disease. The proven ability of sunitinib to target VEGF target kinases suggests that the pseudo-hypoxic drive found in pheochromocytomas/ paragangliomas is identical to the VHL related consequences found in renal cell carcinomas.

The treatment of choice for paraganglioma is surgical resection. While many tumors are benign and can be excised totally, some can be malignant and behave aggressively. Following primary surgery, should this be technically feasible, annual biochemical testing is often done to help rule out metastatic disease, tumor recurrence or delayed appearance of multiple primary tumors. Metastases usually present within 5 years after primary surgery, but may also occur after a very long time in individual patients. Well-recognized risk factors for malignant disease are large tumor size (>5 cm) and tumors with extra-adrenal location

The 5-year survival for patients with malignant PC/PG and distant metastases is less than 50%, but the individual course of disease is highly variable. Radical surgery can be difficult to perform on account of distant metastases, often localized to the skeleton (70%). In metastatic PC/PG, the main therapeutic goal is often to obtain tumor bulk reduction and subsequent control of hypertension. In the palliative treatment of neuroendocrine tumors it has been suggested that if the main tumor bulk (80–90%) can be safely excised, this is a recommended therapy. There are no randomized trials demonstrating any survival advantage of debulking (cytoreductive surgery), however a reduced tumor volume may facilitate subsequent radio- or chemotherapy. Tumor reduction can also be achieved by other interventional techniques such as selective embolization, chemo-embolization, external beam radiation (effective for bone pain), cryoablation, and radiofrequency ablation.

The potential utility of an agent that achieves reproducible responses in these tumours is also high; it may facilitate surgery, complement cytoreductive techniques, reduce morbidity associated with catecholamine excess and potentially extend survival in metastatic disease. Furthermore, compared to chemotherapy, sunitinib is generally well tolerated and can be administered for prolonged periods. Therefore should its efficacy be established in PG/PC, it may provide the opportunity for patients to obtain enduring disease control.

#### 3.0 HYPOTHESIS

That sunitinib will demonstrate clinically useful activity in metastatic pheochromocytoma/ paraganglioma

#### 4.0 TRIAL DESIGN

This is a non-randomized, non-blinded phase II trial of sunitinib in patients with advanced or metastatic recurrent paraganglioma or pheochromocytoma.

### 5.0 STUDY POPULATION

Canada has a universal public health care policy ensuring equal access to health services for all populations and minorities. The population will be defined by the inclusion criteria.

This clinical study will be centred at Princess Margaret Cancer Centre in Toronto, Ontario, and will include Hopital Notre Dame, in Montreal, Quebec and the Alberta Health Services, Calgary, Alberta as participating centres.

### 5.1 Inclusion Criteria

- 5.1.1 Histologically or cytologically confirmed diagnosis of malignant paraganglioma or pheochromocytoma and either evidence of metastases or unresectability.
- 5.1.2 Evidence of recent disease progression radiologically or biochemically or patients with problematic tumourrelated symptoms despite lack of documented recent radiological or biochemical progression
- 5.1.2.1 Radiological disease progression will be defined as follows; when any set of paired CT scans of the chest, abdomen and pelvis (done within 13 months of each other) are retrospectively reviewed and there is progression as evidenced by either any new lesions or at least a 20% increase in the sum of the LD (longest diameter) of target lesions (that will then go on to be followed in the trial), taking as reference the smallest sum LD recorded within the preceding 13 months.
- 5.1.2.2 Biochemical disease progression will be defined as follows; when rate of change equals or exceeds 50% increase over a 6 month +/- 1 month period of either or any of 24-hour urinary metanephrines, catecholamines or serum chromogranin A
- 5.1.2.3 Symptomatic criteria is intended to capture patients whose paraganglioma is clearly causing symptoms to patient or clinical signs concerning to the investigator despite the absence of prior documentation of radiological or symptomatic progression. This would include newly diagnosed patients with concerning signs or symptoms. Investigators will still attempt to document radiological or biochemical progression if possible, as many patients will meet several criteria.

Note: eligibility clarifications settled by PI.

- 5.1.3 Measurable disease defined as that which can be measured in at least one dimension (LD to be recorded) with a minimum size of 10 mm by CT scan
- 5.1.4 ECOG 0-2
- 5.1.5 Life expectancy of greater than 24 weeks.
- 5.1.6 Age > 18 years. (There are no dosing or adverse event data currently available on the use of sunitinib in patients < 18 years of age, therefore patients in this age group are excluded from this study)
- 5.1.7 Patients must have normal organ and marrow function
- 5.1.8 Patients must have PT/INR/PTT within 1.2 X the upper limit

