#### 10.2.1 Measurable Disease.

Measurable tumour lesions are defined as those that can be accurately measured in at least one dimension (longest diameter to be recorded) with a minimum size of 10 mm by CT scan (CT scan thickness no greater than 5 mm), 10 mm caliper measurement by clinical exam or 20 mm by chest X-ray. Malignant lymph nodes considered to be pathologically enlarged and measurable, must be  $\geq$  15 mm in short axis when assessed by CT scan.

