#### 10.2.2 Non-measurable Disease.

All other lesions (or sites of disease), including small lesions (longest diameter < 10 mm or pathological lymph nodes with  $\geq$  10 to < 15 mm short axis) as well as truly non-measurable lesions. Lesions considered truly non-measurable include: leptomeningeal disease, ascites, pleural/pericardial effusions, lymphangitic involvement of skin or lung, inflammatory breast disease, abdominal masses/abdominal organomegaly identified by physical exam that is not measurable by reproducible imaging techniques.

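### Entry counts any 10 mm lesion on CT as measurable, but the endpoint section requires 15 mm short axis for lymph nodes, so a patient with only small nodes can enter with no target lesion and no defined non-progressing outcome

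*Combined protocol and SAP*

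**What the plan says.** All references are to the combined protocol and SAP.

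**Entry.** Criterion 5.1.3 accepts disease that is measurable in "one dimension (LD to be recorded) with a minimum size of 10 mm by CT scan". It gives no nodal threshold and does not refer to section 10. The Trial Summary says only "Unidimensionally measurable disease". For radiological progression at entry, 5.1.2.1 uses "at least a 20% increase in the sum of the LD (longest diameter) of target lesions", again with no short-axis rule for nodes, and says that these same lesions will be followed in the trial.

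**Endpoint.** Section 10.2.1 has a separate nodal rule: "Malignant lymph nodes considered to be pathologically enlarged and measurable, must be" at least "15 mm in short axis when assessed by CT scan". Section 10.2.2 classes pathological nodes from 10 mm up to, but not including, "15 mm short axis) as well as truly non-measurable lesions" as non-measurable. Section 10.2.3 allows a node as a target lesion only from 15 mm short axis and puts the short axis of nodes into the sum. Section 10.2.4 makes all other lesions non-target.

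**Counting.** Section 10.1.2 makes a patient evaluable for response after two cycles and a re-evaluation, or on early objective progression; it does not ask for a target lesion. Section 11.2 defines the primary endpoint, the clinical benefit rate (CBR), as CR, PR, or SD for at least 12 weeks. Section 11.3 stops at 0 of 14 and accepts the drug at 3 or more of 28, counted on the CBR.

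**The concern.** Entry and endpoint use different definitions of measurable disease, and they disagree for lymph nodes. The entry rule can therefore admit a patient for whom section 10 provides nothing to measure. That patient still enters both decision denominators, and the plan does not say whether a non-progressing course counts as a success or a failure.

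The decision rule turns on very small counts: none against one at stage 1, and two against three at the end. One patient scored by local judgement can move either decision, in either direction.

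**Working it through.** **1. Can such a patient enter?** Take a patient whose only lesions are nodes with longest diameter of at least 10 mm and short axis under 15 mm.

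- 5.1.3: met, because one dimension reaches 10 mm on CT.
- 10.2.1 and 10.2.2: not measurable.
- 10.2.3 and 10.2.4: no target lesion; all lesions are non-target.
- 10.1.2: evaluable after two cycles and re-evaluation.

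**2. What can the 10.2.5 table return?**

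| Outcome | What the row needs in the target column | Available without target lesions? |
|---|---|---|
| CR | Target CR | No |
| PR | Target CR or PR | No |
| SD | Target SD | No |
| NE | Targets not all evaluated | Not by its wording, which presupposes targets |
| PD (target growth) | Target PD | No |
| PD (non-target progression) | Any status | Yes |
| PD (new lesion) | Any status | Yes |

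The patient can be scored PD. No row fits if the nodes shrink or stay stable.

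**3. The plan's own operating characteristics.** Inputs from 11.3: 14 + 14 patients, stop at 0 of 14, accept at 3 or more of 28, rates 5% and 20%. With X(n) binomial,

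P(accept) = P(X(28) ≥ 3) − P(X(14) = 0) × P(X(14) ≥ 3).

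- At 20%: 0.9388 − 0.0440 × 0.5520 = 0.915 (stated 0.92).
- At 5%: 0.1627 − 0.4877 × 0.0301 = 0.148 (stated 0.14).

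The power agrees to within a point. The alpha is slightly off, which does not bear on this point.

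**4. If the patient counts as a failure.** The number able to succeed becomes n1 + n2 with the affected patients removed; the thresholds do not change. The same formula at 20% gives:

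| Affected patients | n1 + n2 able to succeed | Power |
|---|---|---|
| None | 14 + 14 | 0.915 |
| One, in stage 1 | 13 + 14 | 0.898 |
| One, in stage 2 | 14 + 13 | 0.906 |
| One per stage | 13 + 13 | 0.889 |
| Two per stage | 12 + 12 | 0.855 |

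The chance of a false stop at stage 1 rises from 0.8^14 = 0.044 to 0.8^13 = 0.055 with one such patient in that stage.

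**5. If the patient is recorded as SD for at least 12 weeks.** Suppose this happens to one stage 1 patient, that the success is certain, and that the other 27 have a true rate of 5%. The 0/14 stop, which would otherwise occur with probability 0.95^14 = 0.488, can no longer occur. Acceptance needs only 2 of the remaining 27:

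1 − 0.95^27 − 27 × 0.05 × 0.95^26 = 1 − 0.250 − 0.356 = 0.394, against 0.148.

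This is an upper illustration, because it treats the stable outcome as certain.

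**The case against.** Several points on the other side are sound.

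- **The response table.** A reader might infer that the table cannot classify such a patient at all. It can: two rows accept any target status and give PD. Only the non-progressing outcomes are missing.
- **Who is affected.** A reader might extend the problem to every patient with node-only disease. Section 10.2.3 does not support that: one node of at least 15 mm short axis gives the patient a target lesion.
- **Which endpoint.** A reader might argue the harm from the patient's inability to reach PR and quote the power loss as the result. Section 11.3 counts successes on the CBR, which includes SD for at least 12 weeks. The SD definition in 10.2.5 opens with a general description of steady disease, so an investigator could record SD. The power loss holds only if the patient is scored a failure; otherwise the error runs the other way.
- **Safeguards.** The note under 5.1.2 leaves eligibility clarifications to the principal investigator. Section 7.2 has a central checklist review. Section 6.0 asks for all measurable and non-measurable disease at screening, and 10.2.3 has targets identified at baseline. A careful site may well notice that there is no target.

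The safeguards lower the chance of a case but do not put the nodal rule into 5.1.3. Section 7.2 says that the criteria must be met without exception, and this patient meets them as written. Section 10.2 adopts RECIST 1.1 for response and progression, not for entry.

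**Conclusion.** Wrong as written: an internal inconsistency between the entry criterion and the endpoint definitions, limited to patients whose every lesion is a node under 15 mm short axis. For them the CBR contribution is undefined unless they progress.

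The size is modest. Scored as a failure, one patient overall costs 1 to 2 points of power (0.915 to 0.898–0.906), and one per stage costs under 3 points (0.889). Scored as stable for 12 weeks, one stage 1 patient removes the futility stop and supplies a third of the evidence needed for acceptance.

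These figures take the plan's 5% and 20% rates as CBR rates and assume the number of affected patients. The documents give no frequency, and it is probably small; two per stage (4 of 28) has no support in them. The case for a change rests on the conflict in the text and the low acceptance threshold, not on a demonstrated loss of power.

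**What to change.** Keep the CT requirement in 5.1.3 and add the nodal rule: at least one lesion measurable by CT as defined in 10.2.1, meaning 10 mm or more in longest diameter for non-nodal lesions and 15 mm or more in short axis for lymph nodes. Make the same change in the eligibility checklist.

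A bare reference to 10.2.1 would not do. That section also accepts lesions measured by caliper or chest X-ray, which would widen entry beyond the present CT rule.

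Align the sum in 5.1.2.1 with 10.2.3, using short axis for nodes, so that lesions judged for progression at entry are measured as they will be in the trial.

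Cost: two lines of text and the checklist, with no change to the sample size or the decision rule. An occasional patient with only small nodes becomes ineligible. The reference also brings the 5 mm slice-thickness condition of 10.2.1 into entry.

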### 5.1.9 Previous Therapy

Radiation: Patients may have had prior radiation therapy. A minimum of 28 days must have elapsed between the end of radiotherapy and registration onto the study. Radiation must have involved < 30% of functioning bone marrow and there must be measurable disease outside the previously irradiated area (patients whose sole site of disease is in a previously irradiated area are ineligible UNLESS there is evidence of progression, or new lesions have been documented, in the irradiated field). Patients must have recovered from any acute toxic effects from radiation prior to registration. Previous Surgery: Previous major surgery is permitted provided that it has been at least 28 days prior to patient registration and that wound healing has occurred.

5.1.10 Laboratory Requirements (must be done within 7 days prior to registration)

Parameter	Limit
granulocytes (AGC)	$> 1.5 \times 10^9 / L$
platelets	$> 100 \times 10^9 / L$
bilirubin	< 1.5xULN
AST and ALT	< 2.5 x ULN
Amylase	<1.5xULN
Lipase	<1.5xULN
Calcium	< 3 mmol/L
creatinine	< 2.0xULN

- 5.1.11 Patient consent must be obtained according to local REB. The patient must sign the consent form prior to randomization or registration.
- 5.1.12 Patients must be accessible for treatment, response assessment and follow-up. Investigators must assure themselves the patients registered on this trial will be available for complete documentation of the treatment, adverse events, and follow-up.
- 5.1.13 Protocol treatment is to begin within 3 working days of patient registration.

#### 5.2 Exclusion Criteria

- 5.2.1 History of other malignancies, except: adequately treated non-melanoma skin cancer, curatively treated in-situ cancer of the cervix, or other solid tumours curatively treated with no evidence of disease for > 5 years or other malignancies associated with the same genetic syndrome.
- 5.2.2 Patients with known brain metastases. (A head CT is not necessary to rule out brain metastases, unless there is clinical suspicion of CNS involvement). Patients with known brain metastases will be excluded from this trial due to their poor prognosis and their likelihood of developing progressive neurologic dysfunction that would confound the evaluation of neurologic and other adverse events.
- 5.2.3 History of allergic reactions attributed to compounds of similar chemical or biologic composition to sunitinib.
- 5.2.4 Patients receiving concurrent treatment with other anti-cancer therapy given for paraganglioma or pheochromocytoma or other therapy or other investigational anticancer agents.
- 5.2.5 Patients who have received prior treatment with any other antiangiogenic agent or multi-targeted tyrosine kinase inhibitors (e.g., bevacizumab, sorafenib, pazopanib, thalidomide, AZD6474, AMG706, AZD2171, PTK787, VEGF Trap, etc.) are ineligible.
- 5.2.6 Patients with any of the following cardiovascular findings are to be excluded:
  - 5.2.6.1 QTc prolongation (defined as a QTc interval equal to or greater than 500 msec) or other significant ECG abnormalities. An ECG must be done within 21days prior to registration and as clinically indicated.
  - 5.2.6.2 Current or history of Class III or IV heart failure as defined by the NYHA functional classification system (see Appendix V).
  - 5.2.6.3 Patients with prior anthracycline exposure, previous central thoracic radiation that included heart in radiation port, or a history of NYHA Class II cardiac function UNLESS
    - They are currently asymptomatic with respect to cardiac function AND
    - LVEF as assessed by MUGA at baseline is > lower limit of normal (LLN) of institution. The MUGA must be done within 21 days prior to registration.
  - 5.2.6.4 Poorly controlled hypertension (systolic blood pressure of 150 mmHg or higher or diastolic blood pressure of 90 mmHg or higher)
  - 5.2.6.5 Myocardial infarction, cardiac arrhythmia, stable/unstable angina, symptomatic congestive heart failure, or coronary/peripheral artery bypass graft or stenting within 12 months prior to study entry
  - 5.2.6.6 History of venous thrombosis or pulmonary embolism in the past 3 months
  - 5.2.6.7 History of cerebrovascular accident (CVA) or transient ischemic attack within 12 months prior to study entry
- 5.2.7 Patients who require use of therapeutic doses of coumarin-derivative anticoagulants such as warfarin are excluded, although doses of up to 2 mg daily are permitted for prophylaxis of thrombosis. Note: Low molecular weight heparin is permitted provided the patient's INR is < 1.5. INR must be done within 7 days prior to registration.
- 5.2.8 Patients with bowel obstruction or any condition (e.g. gastrointestinal tract disease resulting in an inability to take oral medication or a requirement for IV alimentation, prior surgical procedures affecting absorption, or active peptic ulcer disease) that impairs their ability to swallow and retain sunitinib tablets.

- 5.2.9 Patients with serious illness or medical condition which would not permit the patient to be managed according to the protocol including, but not limited to:
  - History of significant neurologic or psychiatric disorder which would impair the ability to obtain consent or l imit compliance with study requirements
  - Active uncontrolled infection
  - Any other medical conditions that might be aggravated by treatment
  - Serious or non-healing wound, ulcer, or bone fracture.
  - Abdominal fistula, gastrointestinal perforation, or intra-abdominal abscess within 28 days of treatment.
- 5.2.10 Use of agents with proarrhythmic potential (amiodarone terfenadine, quinidine, procainamide, disopyramide, dofetilide, dronedarone, ibutilide, sotalol, probucol, bepridil, haloperidol, risperidone, indapamide and flecainide) is not permitted during the study. A comprehensive list of agents with proarrhythmic potential can be found at http://crediblemeds.org.
- 5.2.11 Because sunitinib is metabolized primarily by the CYP3A4 liver enzyme the concomitant use of certain drugs is prohibited. Patients receiving List A drugs below are not eligible unless > 7 days since last dose before starting sunitinib and no dosing during the trial. Patients receiving List B drugs below are not eligible unless > 12 days since last dose before starting sunitinib and no dosing during the trial. A comprehensive list of medications and substances known or with the potential to alter the pharmacokinetics of sunitinib through CYP3A4 is provided in Appendix VI.

